7.5.1. Breaking the Blind

Breaking the treatment blind for a patient should be done only in the event of a medical emergency where the identity of the IP is necessary to appropriately treat the patient. The Investigator may unblind the treatment received by the patient through the interactive response technology (IRT). The IRT will automatically document and record any such unblinding and notify the Sponsor Medical Monitor of the unblinding event. If possible, the Sponsor and/or designee should be contacted prior to unblinding of the treatment. The study monitor will not be apprised of the actual treatment assignment.

7.6. Treatment After the End of the Study

All patients completing the End of Study Visit (Visit 14, Week 34) may be offered enrollment in the long-term extension study (SCOUT-016).

8. STUDY DRUG MATERIALS AND MANAGEMENT

8.1. Description of Investigational Product

RAD011 is an oral CBD solution in which CBD is solubilized in MCTs. Cannabidiol is classified as a phytocannabinoid with a low affinity for the cannabinoid receptors CB1 and CB2. Although CBD has a low affinity for CB1 receptors (Petitet, 1998; Thomas, 1998), it has demonstrated antagonism for CB1 receptor agonists (Pertwee, 2002; Zuardi, 1981). Table 8 presents an overview of the IP. Cannabidiol Oral Solution 100 mg/mL formulation contains vitamin E (DL-alpha-tocopherol) as an antioxidant, saccharin as a sweetener, strawberry flavor, and MCTs.

Refer to the Investigator's Brochure for a detailed description of RAD011. Refer to the Pharmacy Manual for detailed instructions on preparation, handling, storage, and accountability of RAD011.

Table 8: Investigational Product

Investigational Product		
Product Name:	RAD011	Placebo
Dosage Form:	Oral solution	Oral solution
Unit Dose	30 mL vial at a concentration of 100 mg/mL	30 mL vial with vehicle
Route of Administration	Orally	Orally
Physical Description	Clear, colorless to pale yellow to pinkish brown solution, free of visible particles. Medium chain triglycerides (Miglyol 812N) are used as the vehicle to dissolve cannabidiol Saccharin concentration of 0.24 mg/mL	Clear, colorless to pale yellow to pinkish brown solution, free of visible particles. Medium chain triglycerides (Miglyol 812N) are used to formulate the placebo formulation Saccharin concentration of 0.24 mg/mL
Manufacturer	Benuvia Manufacturing	Benuvia Manufacturing

8.2. Study Drug Packaging and Labeling

RAD011 (100 mg/mL) finished drug product is filled into 30 mL amber-colored screwcap glass bottles and capped with a 20-mm child resistant white polypropylene cap. The placebo will be provided in identical, amber-colored screwcap, child-resistant glass bottles.

Investigational product will be released to the site upon receipt of all required essential documents. All medication provided to the study site will be prepared, packaged, and labeled by the Sponsor according to Standard Operating Procedures (SOP), Good Manufacturing Practices (GMP), and applicable local laws and regulations.

8.3. Study Drug Storage

The IP is shipped to the site at 2 to 8°C (36 to 46°F). While at the site, IP must always be stored in a refrigerated (2 to 8°C [36 to 46°F]) secure location with limited access. To ensure adequate storage in the home setting, IP is recommended to be stored in the caregiver's refrigerator. Additional information on stability is provided in the Pharmacy Manual.

8.4. Study Drug Preparation

Investigational product will be obtained from the vial using a plastic syringe provided by the Sponsor. The dose will be ejected from the plastic syringe into a dosing cup. Investigational product must be administered orally directly and not mixed with food or other liquids prior to administration. Patients should take the IP with food.

8.5. Study Drug Accountability

The Investigator is required to maintain adequate records of the disposition of the IP, including kit numbers, the date and quantity of drug received, the time, date, and volume to whom it was dispensed, and a detailed accounting of any drug accidentally or deliberately destroyed.

Drug accountability will be measured at every in-person visit by weighing and counting the number of bottles returned by the patient at each visit. Patients will be required to retain and return all empty and partially filled bottles at each study visit. Additional details on drug accountability are provided in the Pharmacy Manual.

Records for storage, preparation, and dispensing of IP must be available for inspection by the Sponsor throughout the study.

8.6. Study Drug Handling and Disposal

Unused IP will be returned to the Sponsor at the conclusion of the study, or destroyed according to the site's SOPs, as mutually agreed between the Sponsor and the Site.

Bottles of IP returned by patients may be destroyed per the site's SOPs once accountability has been completed.

9. ASSESSMENT OF EFFICACY

Questionnaires completed by the patients, or their caregivers are used to assess primary, secondary, and other endpoints. The same caregiver should complete the questionnaires with the patient every time the questionnaires are administered.

9.1. Primary Efficacy Endpoint (HQ-CT Questionnaire)

The primary efficacy endpoint for this study is the change in HQ-CT scores from Baseline through End of Study/Week 34 Visit for RAD011 compared to placebo. The HQ-CT questionnaire is a tool that was developed specifically for use in patients with PWS and was validated in this population as a 13-item questionnaire (Dykens, 2007). The original tool was further refined and validated and now consists of 9 items, with a 2-week recall period. Each question is rated on a scale of 0 to 4, therefore providing a maximum score of 36. An HQ-CT score of 13 is associated with moderate to severe hyperphagia (Fehnel, 2015).

The HQ-CT questionnaire was selected as the primary endpoint since it has been validated in patients with PWS and is the gold standard outcome measure in studies evaluating hyperphagia-related behavior (Allas, 2018; McCandless, 2017). Additionally, this tool has recently been reported to have a strong correlation to caregiver burden, further supporting the clinical relevance of the HQ-CT questionnaire in this study (Kayadjianian, 2021).

9.2. Secondary Efficacy Endpoints

9.2.1. Change in Irritability (Irritability subscale of the ABC Questionnaire)

A secondary endpoint of this study is to evaluate the change in PWS-associated irritability from Baseline through End of Study/Week 34 Visit using the irritability subscale of the ABC questionnaire. In patients with PWS, anxiety manifests as irritability. The ABC questionnaire is an informant-rated questionnaire assessing severity of behavioral symptoms, is one of the few empirically developed scales designed to measure psychiatric symptoms and behavioral disturbance exhibited by individuals with developmental disabilities (intellectual disability, autism spectrum disorder, cerebral palsy, epilepsy). According to factor analyses, there are five subscales: (a) irritability and agitation, (b) lethargy and social withdrawal, (c) stereotypic behavior, (d) hyperactivity and noncompliance, and (e) inappropriate speech (Aman, 1987). The ABC originally was developed to assess the effectiveness of psychotropic medication, and has been used extensively in pediatric, as well as adult behavioral and psychiatric research due to its high reliability and validity. The Irritability subscale of the ABC covers symptoms such as agitation, aggression, meltdowns, and self-harm. An extensive psychometric assessment of the ABC has indicated that the subscales have high internal consistency, good reliability, and established validity. For this reason, the Irritability subscale of the ABC questionnaire is being proposed to evaluate PWS-associated anxiety, manifesting as irritability, as a secondary outcome. Anxiety and irritability associated with PWS is of significant concern to patients and to their caregivers and represents an unmet medical need (Aman, 1995; Aman, 1987; Aman, 1985; Aman, 1985).

Overall, the ABC contains 58 items divided in 5 subscales, and the Irritability subscale contains 15 items. Each item is scored as 0 (never a problem), 1 (slight problem), 2 (moderately serious problem), or 3 (severe problem). Items load onto one of five empirically derived subscales: Irritability, Agitation, & Crying (15 items); Lethargy/Social Withdrawal (16 items); Stereotypic Behavior (7 items); Hyperactivity/Noncompliance (16 items); and Inappropriate Speech (4 items). In addition, a Total Score can be calculated. The ABC questionnaire has a recall period of 1 month, and has also successfully been used in patients with PWS (Clarke, 1996; Consoli, 2019; Ishii, 2017; Salehi, 2018).

9.2.2. Change in Clinician Global Impression of Change in Hyperphagia (CGI-C Questionnaire)

A secondary endpoint of this study is to evaluate the change in hyperphagia as defined by the CGI-C in Hyperphagia response through End of Study/Week 34 Visit. The CGI scales have been found to be valid as an external criterion in symptom improvement and to correlate significantly with self-rated and other valid scales of symptom severity (Khan, 2002; Leon, 1993). Clinical Global Impression scales have also been used successfully in evaluating therapeutic responses in patients with PWS (Avrahamy, 2015; Consoli, 2019; Dykens, 2018).

9.2.3. Change in Clinician Global Impression of Severity of Hyperphagia (CGI-S Questionnaire)

A secondary endpoint of this study is to evaluate the change in severity of hyperphagia as defined by the CGI-S response from Baseline through End of Study/Week 34 Visit.

9.3. Other Endpoints

9.3.1. Change in Caregiver Global Impression of Change in Hyperphagia, Change in Caregiver Global Impression of Severity of Hyperphagia, Change in Caregiver Global Impression of Change in Irritability

Caregiver global impression scales of severity and change specific to hyperphagia and change in irritability will be other endpoints in this study. They will be assessed through the End of Study/Week 34 visit.

9.3.2. Change in Overall Behavior (ABC)

Change in overall behavior from Baseline through End of Study/Week 34 Visit in response to RAD011 compared to placebo will also be considered an endpoint in this study. The remaining ABC subscales (described in [Section 9.2.1](#)) will be used to assess overall behavior.

9.3.3. Change in Sleep (ESS-CHAD Questionnaire)

An other endpoint is the change in the ESS-CHAD questionnaire from Baseline through End of Study/Week 34 Visit. The ESS-CHAD is an 8-question scale with a 1-month recall period that has been validated in school-attending children and adolescents to evaluate daytime sleepiness ([Janssen, 2017](#)). Each question is rated on a 0 to 3 scale, with a maximum score of 24, and a score above 10 is considered to represent mild excessive daytime sleepiness.

9.3.4. Change in Body Mass Index and Weight

Changes in BMI and weight through End of Study/Week 34 Visit will be evaluated as an other endpoint. Change in age-normalized BMI z-scores ([USPSTF, 2017](#); [Wei, 2020](#)) will be used for patients aged 8 to 19 years inclusively, whereas percent change in weight will be used for patients aged 20 to 65 years.

9.3.5. Change in Skin-Picking Behavior

An other endpoint in this study is to evaluate the change in skin-picking behavior between scale values across time points using the Skin Picking questionnaire from Baseline through End of Study/Week 34. The Skin Picking questionnaire is a 6-item questionnaire of skin picking symptoms, with scores ranging from 0 to 24 ([Keuthen, 2001](#)). A score of ≥ 7 is considered highly suspicious for a skin picking disorder.

9.3.6. Change in Muscle/Fat Composition (DEXA Scan)

Change in muscle/fat composition using a DEXA scan from Visit 5 through End of Study/Week 34 visit will also be an other endpoint. The assessment of change in muscle/fat composition will be performed at a selected number of US sites only. All attempts should be made to have both DEXA scans performed at the same site using the same DEXA scanner, and DEXA scans of children and adolescents should be interpreted only by providers experienced in scoring DEXA scan in this patient population. Results of the DEXA scan will be reported as percentage body fat. The DEXA scan may be performed within ± 7 days of Visits 5 and 14.

9.4. Pharmacokinetic Endpoints

Throughout the study, plasma samples will be collected to establish the PK profile of CBD and 2 metabolites, 7-OH-CBD and 7-COOH-CBD in patients with PWS. Furthermore, an exposure-response analysis using CBD and 7-OH-CBD concentrations as well as a population PK model will be derived from the data. Details on sample collection are provided in [Section 10.1.13](#) and in the Laboratory Manual.

9.5. Biomarkers assessments (Phase 3 exploratory)

For Phase 3 patients: If the patient/legal guardian consents, samples will be collected for exploratory assessment of biomarkers. Blood samples will be collected at Visit 1 and Visit 14 and stored for potential exploratory analysis of biomarkers (including but not limited to inflammation). Details on sample collection are provided in the Laboratory Manual. No genetic or DNA analysis will be conducted on the samples.

10. ASSESSMENT OF SAFETY

10.1. Safety Parameters

10.1.1. Demographics and Medical/Surgical/Seizure History

Demographic characteristics will be collected during the Screening Visit (Visit 1). A full medical/surgical history (including seizure history) will also be documented at the Screening Visit (Visit 1). Evaluation of seizure history and Seizure Patient Impression are provided in [Appendix 2](#).

10.1.1.1 Seizure Patient Impression

Patients with a history of seizure who are randomized will be evaluated for potential changes in seizure activity at the End of Study/Week 34 Visit as detailed in [Appendix 2](#).

10.1.2. Vital Signs

Vital signs to be collected include BP, HR, RR, oxygen saturation, and temperature. Blood pressure and pulse measurements may be assessed using an automated device or by manual techniques. Vital signs should be collected after the patient has rested (per standard of care) and prior to blood draws for laboratory tests.

10.1.3. Weight and Height

Height and weight will be collected as identified in the Schedule of Assessments tables ([Table 6](#) and [Table 7](#)). Both height and weight must be collected per the Schedule of Assessments as BMI Z-scores will be computed for children and change from baseline will be computed for adults (see the SAP for additional information). Efforts should be made to use the same scale throughout the project when possible.

10.1.4. Physical Examination

A full physical examination will be performed at Screening Visit 1 (Visit 1) and at Visit 5 (Week 7). All other physical examinations should be abbreviated, symptom directed physical examinations. The Investigator is responsible for conducting the exams, determining findings, assessing abnormalities, and evaluating clinical significance.

10.1.5. Electrocardiogram

A 12-lead ECG will be performed after the patient has rested in a supine position.

10.1.6. Columbia Suicide-Severity Rating Scale

The C-SSRS is a broadly validated scale aimed at assessing suicidal risk in a variety of children and adult populations. The scale includes suggested questions to solicit the type of information needed to determine if suicidal ideation and/or behavior occurred. Administration of the C-SSRS should occur after nonleading AE collection, and findings from the C-SSRS should not be included as an AE unless it leads to study discontinuation. The first time the C-SSRS questionnaire is administered, on Visit 5 (Week 7), the Baseline/Screening questionnaire ([Posner, 2008](#)) should be used, and the “Since Last Visit” questionnaire should be used for all subsequent assessments.

The standard C-SSRS scale should be used for patients aged 6 and over and the Children’s C-SSRS scale should be used in patients aged less than 6 years. However, the Children’s version may be used in patients aged 6 years or older when the Investigator or designee determines that the patient is unable to understand the first couple of questions in the standard version. The same C-SSRS scale should be used for a given patient throughout the study.

If a suicidal behavior is identified during the study, the Investigator must provide immediate care and refer the patient to additional care as needed.

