5.8.3.1 Visits 2 to 4 (Weeks 1 to 6)

The following assessments must be performed in person during Visits 2 to 4 (Weeks 1 to 6):

- Review of concomitant medications

- Review of AEs
- Weight and height
- Vital signs, including, BP, HR, temperature, RR, and oxygen saturation
- Completion of the HQ-CT questionnaire
 - The same caregiver should be available throughout the study to complete the questionnaires with the patient
 - At Visit 2, HQ-CT must be completed pre-dose
- Review of HQ-CT questionnaire scores for eligibility (Visit 2 only)
 - The electronic data capture (EDC) system will automatically calculate mean HQ-CT score from Visit 1 and Visit 2. Patients with a mean HQ-CT score ≥ 13 will be eligible to continue in the Tolerability Period. Further details are described in [Section 6.4](#)
- Completion of the and Epworth Sleepiness Scale for Children and Adolescents (ESS-CHAD), CGI-S Hyperphagia, Skin Picking, and Columbia Suicide Severity Rating Scale (C-SSRS) questionnaires (predose-, only to be performed at Visit 2)
- Placebo dispensing (Visit 2 only)
- Placebo dosing (Visit 2 only)
- Drug accountability (only Visits 3 and 4)
- Food Diary Reminder and Food Diary Distribution (only Visit 4).

5.8.4. Dose Escalation Period (3 weeks, Visits 5 to 7 [Weeks 7 to 10])

The Schedule of Assessments table for the Dose Escalation Period is provided in [Table 7](#).

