10.2.1.5 Adverse Events of Special Interest (AESI)

An AESI is an adverse event (AE) that is designated to be of special medical or scientific interest to the Sponsor. All AEs within the category of AESIs should be reported promptly, following the reporting procedures for abnormal laboratory, AEs or SAEs as appropriate.

1. Suicide ideation and behavior AESI

Included in this AESI are adverse events following administration of RAD011 that are assessed by the Investigator to be any of the following: suicidal ideation, suicidal behavior, suicide attempt, and completed suicide.

2. Hepatic dysfunction AESI

Included in this AESI are abnormal laboratory findings or adverse events suggestive of hepatic dysfunction following administration of RAD011 such as greater or moderate elevation of liver enzymes (AST, ALT, ALP, gamma-glutamyl transferase [GGT]) and bilirubin; or adverse events of right upper quadrant abdominal pain, chronic fatigue, loss of appetite, unexplained nausea and vomiting, yellowing of skin or eyes, itching, dark urine, and light-colored stools.

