10.2.2. Collection and Recording of Adverse Events

All patients will be monitored closely for AEs/SAEs during study participation. Sources for AE/SAE notification include patient self-reports, abnormalities found on physical assessments, imaging, or other clinical investigations, clinical laboratory exam results, and other sources relating to the patient's health that becomes available to the Investigator. The Investigator should take all appropriate measures to ensure the safety of patients and should follow up the outcome of all AEs (clinical, laboratory values, or other, etc.) until the return to normal or until the patient's condition has stabilized. In the event of an SAE, the Investigator should follow up for the outcome until the clinical recovery is complete and laboratory results have returned to normal or until progression has been stabilized.

All AEs/SAEs will be entered into the electronic database. All AEs/SAEs will be collected from the time of ICF signature up to completion of the EOS/Week 34 Visit for patients enrolling in the long-term extension study (SCOUT-016) or up to Week 38Visit for patients entering the Taper and Follow Up Periods. Patients who discontinue prematurely from the study will be encouraged to return for assessment of safety. Follow up safety information may also be obtained from a patient's physician or medical records.

All AEs/SAEs spontaneously reported by the patient and/or in response to an open question from study personnel or revealed by observation, physical examination, or other diagnostic procedures must be recorded in the source document and on the appropriate page of the eCRF. Any clinically relevant deterioration in laboratory assessments or other clinical findings is considered an AE and must be recorded on the appropriate pages of the eCRF. When possible, signs and symptoms indicating a common underlying pathology should be noted as one comprehensive event. Documentation of time of onset, time of resolution, seriousness assessment, maximal severity assessment, relationship assessment, action taken, treatments administered, and outcomes must be provided on the AE CRF and SAE form.

All SAEs that occur during the course of the study, as defined by the protocol, must be reported by the Investigator to Radius by completing and emailing the SAE Form within 24 hours of the

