11.4.5. Safety Analyses

The Safety Population will be used for all safety assessments. Safety assessments will be based on AEs, C-SSRS, vital signs, ECGs, and laboratory assessments. All analyses of safety will be described in the SAP.

All safety assessments will be descriptive, and no inferential statistics will be performed. All data listings will be provided for protocol specified safety data. The Medical Dictionary for Regulatory Activities will be used to classify all AEs with respect to System Organ Class (SOC) and preferred term. Adverse event summaries will include only treatment-emergent adverse events (TEAEs) by treatment group. Assessment of severity and relationship will also be presented. Adverse events leading to study discontinuation will also be summarized by SOC, PT, severity, and relationship.

The Columbia Suicide Severity Rating Scale will be used to evaluate suicidal ideation and intensity of ideation. Ideation and intensity will be grouped by categories, with separate groupings for the Baseline/Screening and the “Since Last Visit” questionnaires.

Clinical laboratory and vital signs will be summarized for the Safety Population for observed values and change from Baseline. Shifts from Baseline according to normal range criteria will also be presented for all patients in the Safety Population.

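### Section 10.1.6 keeps C-SSRS findings out of the AE data unless the patient leaves the study, which conflicts with the suicidality AESI; it also names the wrong first C-SSRS visit

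*Protocol*

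**What the plan says.** **Recording rule.** Protocol Section 10.1.6 places the C-SSRS after non-leading AE collection and then says that "findings from the C-SSRS should not be included as an AE unless it leads to study discontinuation".

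**AESI.** Section 10.2.1.5 defines a suicidality AESI as adverse events following RAD011 that are "assessed by the Investigator to be any of the following: suicidal ideation, suicidal behavior, suicide attempt, and completed suicide". It adds that "All AEs within the category of AESIs should be reported promptly". It sets no condition about leaving the study.

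**General rule.** Section 10.2.2 says that AEs and SAEs reported by the patient or "revealed by observation, physical examination, or other diagnostic procedures must be recorded in the source document and on the appropriate page of the eCRF". It also requires every SAE to be reported within 24 hours. Neither rule has a C-SSRS exception.

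**First administration.** Section 10.1.6 reads "The first time the C-SSRS questionnaire is administered, on Visit 5 (Week 7" and assigns the Baseline/Screening form to that occasion and the Since Last Visit form to all later ones. Section 5.8.3.1 lists "Columbia Suicide Severity Rating Scale (C-SSRS) questionnaires (predose-, only to be performed at Visit 2", and Table 6 agrees. Section 5.8.4.1 and Table 7 give a further pre-dose C-SSRS at Visit 5.

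**Analysis.** Section 11.4.5 evaluates ideation and its intensity: "Ideation and intensity will be grouped by categories, with separate groupings for the Baseline/Screening" and the Since Last Visit questionnaires. It leaves the detail of the safety analyses to the SAP.

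**The concern.** The C-SSRS is the only instrument in the trial aimed specifically at suicidality, and the suicidality AESI is the category meant to collect such events. A site that follows Section 10.1.6 to the letter does not enter a C-SSRS finding as an AE if the patient stays in the study. The finding then cannot become an AESI, because the AESI is made up of AEs. It would also lack what the AE record supplies under Section 10.2.1: severity, causality, action taken and outcome.

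This matters more here than in many trials. Section 3.1.2 notes that a CB1 antagonist was withdrawn from the market because of psychiatric side effects, and the Phase 2 part exists to choose doses on safety and tolerability.

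The visit conflict is separate and smaller. Sites are told two different things about when the first C-SSRS takes place, and the choice of form depends on which occasion is the first.

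**Working it through.** The point rests on no sample size, power or event figure, so the check is a side-by-side reading.

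**1. Can a C-SSRS finding reach the AESI?**
- Section 10.2.1.5: AESI events are AEs that the investigator judges to be suicidality.
- Section 10.1.6: a C-SSRS finding is not an AE unless it leads to study discontinuation.
- Together: a finding known only from the C-SSRS, in a patient who stays in the study, is not an AE and so cannot be an AESI, although nothing in Section 10.2.1.5 makes leaving the study relevant.
- The condition is study discontinuation. Section 6.3.1 keeps patients who stop the product without withdrawing consent in follow-up, so even stopping treatment would not clearly satisfy it.

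**2. Do the other rules close the gap?** Only in part.
- Section 10.2.1 has patients asked non-leading AE questions at every visit. Suicidality volunteered there is recordable. Section 10.1.6 puts the C-SSRS after that questioning, so what remains exposed is what emerges only on the form.
- Sections 10.2.1.3 and 10.2.2 require reporting of every event that meets a seriousness criterion, including the medically-important criterion. Leaving the study is not one of these criteria. Serious events remain reportable.
- Section 10.2.2 requires recording of AEs found by other diagnostic procedures. Read alone, it would bring C-SSRS findings in. Read with Section 10.1.6, the two instructions conflict.
- Section 11.4.5 summarizes C-SSRS ideation and intensity separately. It does not name behavior, and a summary table does not replace prompt AESI reporting.

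The exposed set is therefore suicidality found only through the C-SSRS, chiefly non-serious, in patients who stay in the study.

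**3. How does the other AESI compare?** Section 10.2.1.5 counts abnormal laboratory findings directly toward the hepatic AESI, and Section 10.1.7 has clinically significant laboratory values recorded as AEs. Only the suicidality instrument is cut off from its own AESI.

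**4. Size.** Among non-serious suicidality events, let q be the share found only on the C-SSRS and d the share of those that lead to study discontinuation. Under Section 10.1.6 read literally, the AE data capture 1 − q(1 − d). Nothing is lost if q = 0 or d = 1; everything is lost if q = 1 and d = 0. The protocol gives neither q nor d, nor any suicidality rate, so no number follows.

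**5. Order of administrations.** Sections 5.8.3.1, 5.8.4.1 and 5.8.5.1 give the C-SSRS at Visits 2, 5, 8, 10, 12 and 14. Visit 5 is second, not first. If the words about the first time govern, the Baseline/Screening form belongs to Visit 2 and the Since Last Visit form to Visit 5. If the visit label governs, the Baseline/Screening form belongs to Visit 5 and no form is assigned to Visit 2.

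**The case against.** The best defense is that the two sections do different jobs. Section 10.1.6 limits when an answer on a solicited scale counts as an AE; Section 10.2.1.5 classifies events that are already AEs, filtered by investigator judgment. On that view there is no literal contradiction, and keeping solicited answers out of AE tables is a way to avoid inflating counts. It stands that the AESI is a subset of AEs and that the investigator must make the assessment. But the limit removes events that the AESI names, on a criterion that the AESI does not use, and it covers behavior and attempts as well as ideation. The C-SSRS is scheduled identically in all arms of a double-blind trial, so solicitation by itself gives no reason to expect unequal ascertainment.

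On the visit, it is fair to say that the form is tied to the first occasion and that the visit number may be the only error. That is a plausible repair, but the text does not settle it.

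Several stronger inferences are tempting and should be resisted:
- *Any suicidality disclosed by a patient who stays in the study escapes AE recording, attempts included, and expedited reporting is lost.* Volunteered events and SAEs remain reportable.
- *The C-SSRS is the only systematic source.* AE questioning at each visit is systematic too; the C-SSRS is the only targeted instrument.
- *The AESI table would show a small fraction of the true count.* No rate in the protocol supports any fraction.
- *Run-in data from Visit 5 are pooled with on-treatment data.* Section 11.4.5 does not say so. It would depend on the form used at Visit 5 and on detail left to the SAP.
- *The DMC would not see these findings.* Section 10.4 gives it safety and tolerability data, not only AE tables; Section 11.4.5 lists the C-SSRS among the safety assessments.

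**Conclusion.** Both inconsistencies are real and should be corrected. Followed literally, Section 10.1.6 could leave suicidality that emerges only on the C-SSRS out of the AE and AESI data, chiefly non-serious events in patients who stay in the study. The size cannot be derived: it could be nil if every such event is also volunteered or leads to study discontinuation. The conclusion rests on sites applying Section 10.1.6 as written rather than the broader recording rule in Section 10.2.2. The first-visit statement contradicts two other places in the protocol and leaves the form at Visits 2 and 5 ambiguous. Neither point touches the primary efficacy analysis.

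**What to change.** Reconcile Section 10.1.6 with Sections 10.2.1.5 and 10.2.2:
- Remove the discontinuation condition for C-SSRS findings that the investigator assesses as meeting the AESI definition, so that these are recorded as AE and AESI, and as SAE if serious.
- Align the first-administration visit in Section 10.1.6 with Section 5.8.3.1 and Table 6, and state which form is used at Visit 2 and which at Visit 5.

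The cost is a few sentences in one section and a note to sites. No assessment is added. The downside is that the suicidality AE count may rise because some reports will be solicited; the safety tables can be read with that in mind.
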